7.1.5 Instructions for Use and Administration

At Visit 1 subjects will be instructed by the dedicated dosing coordinator on appropriate hygiene and eye drop dosing technique. Subjects will self-administer NOV03 or saline eye

drops in each lower cul-de-sac of each eye as shown in Appendix 2 under the supervision of the dedicated dosing coordinator on Day 1 (Visit 1). Subsequent eye drops on Day 1 are to be instilled by the subjects according to detailed written instructions. Subjects will be instructed to instill their drops into both eyes QID for the duration of the trial. Clinic staff will coach the subjects to dose themselves at approximately the same time every day e.g., morning, lunch time/mid-day, afternoon/early evening, and at bedtime. If a dose is missed, then the next dose should be administered on time. The dedicated dosing coordinator will inform subjects on how to store IMP (see Section 7.1.3) and dose IMP and how to complete their dosing diary.

Dosing should be continued until the day of the next Visit (should be at least 2 hours before first ophthalmic examination).

The bottles are designed for multiple use. Subjects will be instructed to only open one bottle at a time. They should be instructed not to discard the empty bottles but keep them in the kit box and return them at their next visit in the kit box. Subjects will record dosing in their dosing diary. Subjects will be instructed not to show the assigned IMP to the Investigator or site staff other than the dedicated dosing coordinator, unless instructed to do so.

7.2 IMP Accountability

The dedicated dosing coordinator at each site must keep an accurate accounting of IMPs received from the supplier by maintaining a detailed inventory. IMP shipment records will be verified and accountability performed by comparing the IMP shipment inventory sheet to the actual quantity of used/unused IMP bottles received at the site.

Accurate records of receipt and disposition of the IMP (e.g. dates, quantity, subject number, kits used, kits unused, etc.) must be maintained by the dedicated dosing coordinator at each site. This includes the amount dispensed to subjects, amount returned to the site by the subjects, and the amount returned to the sponsor or designee upon completion of the trial.

Investigational trial medication orders, records of receipts, dispensing records, and inventory forms will be examined and reconciled by the dedicated dosing coordinator. At each visit, subjects will return all bottles to clinic staff for accountability purposes. Accountability will be ascertained by performing reconciliation between the amount of IMP cartons (kits and their components) sent to the site, the amount used and unused at the time of reconciliation. All investigational trial medication that is dispensed during the course of the trial must be accounted for on an IMP accountability form. No IMP kits or bottles will be returned to the Sponsor prior to full accountability by sponsor's monitor.

7.3 IMP Handling and Return

Unless otherwise directed, at the end of the trial all returned (used and unused) IMP must be directly shipped from the clinical site to the Sponsor for destruction of the medications.

Note: The medications should not be disposed or returned prior to full accountability by the sponsor's monitor. The clinical site will include a copy of all completed drug disposition forms with the IMP to the sponsor after full accountability is completed.

7.4 IMP Masking

Investigational drug and control will be provided in identical bottles and labels to ensure the double-masked character of the trial. The Investigator/site staff and Bausch & Lomb, Incorporated personnel or designee(s) involved in the conduct of the trial will be masked to the IMP. Clinical Trial Material Supply Chain are unmasked designee.

Due to physicochemical differences between NOV03 and saline, there will be a dedicated dosing coordinator who will be responsible for the handling of IMP and activities (such as dispensation, collection, accountability) surrounding the use of IMP.

Each site must have a dedicated dosing coordinator that will be responsible for:

- all IMP dispensation and accountability,
- daily diary dosing education/review,
- all discussions with study subjects related to IMP,
- the administration of the Eyedrop Acceptability and Instillation Comfort Questionnaires.

This designee shall not participate in any other trial procedures and not report this information to other staff. Subjects will be instructed to administer the IMP out of the sight of the Investigator or site staff other than the dedicated dosing coordinator. Subjects are not to show or discuss the properties of the assigned IMP to the Investigator or site staff other than the dedicated dosing coordinator, unless instructed to do so.

7.5 Other Trial Supplies

Diaries, Questionnaires, Urine Pregnancy Tests, Meibomian Gland Evaluator stick, Schirmer's test strips, sodium fluorescein, will be provided to sites. Respective instructions are available in [Appendix 3](#) and manual of operations.

8 TRIAL METHODS AND PROCEDURES

8.1 Concurrent Medications and Therapies

The use of any concurrent medication, prescription or over-the-counter, is to be recorded on the subject's source document and corresponding eCRF along with the reason the medication was taken. Concurrent or previous medications are to be recorded for 60 days prior to Visit 0. Any physical therapies, or surgeries are to be documented for 6 months prior to Visit 0.

Therapy considered necessary for the subject's welfare that will not interfere with the evaluation of the study medication may be given at the discretion of the Investigator and in consultation with the medical monitor. If there is any question as to whether the medication may interfere, the investigator should contact the medical monitor or sponsor. Whenever possible, medications should be administered in dosages that remain constant throughout the study duration.

Physical therapies such as lid scrubs, lid wipes, warm compresses, systemic antibiotics (such as tetracyclines) and oral supplements for treatment of ocular conditions must be stable within the last 30 days prior to Visit 1 and should be maintained stable throughout the trial. Changes in those therapies or initiation of such therapies should be recorded on the subject's source document and corresponding eCRF.

8.2 Prohibited Medications

Disallowed medications and treatments are listed in the exclusion criteria ([Section 5.4](#)). All medications and treatments that were not allowed prior to trial are also not allowed during the trial in particular wearing of contact lenses, ocular surgery/ocular laser treatment of any kind, and no other dry eye treatments such as artificial tears, gels, or ointments or TrueTear™ device (Intranasal Tear Neurostimulator) shall be used within 24 hours prior to Visit 1 and throughout the course of the trial.

Specific prohibitions:

- Topical ocular steroid treatments, topical cyclosporine, lifitegrast, serum tears or topical anti-glaucoma medication within 60 days prior to Visit 0 and during the trial.
- Oral medications known to cause ocular drying (e.g., antihistamines, antidepressants, etc.) on a non-stable regimen within 1 month prior to Visit 0 or expected to be unstable during the trial. Amitriptyline (e.g., Elavil) is only allowed as sleep aid and should not be used within 24 hours prior to any visit (see [Section 8.1](#)).

Concurrent enrollment in another investigational drug or medical device trial is not permitted.

[REDACTED]

[REDACTED] :

[REDACTED]

[REDACTED]

[REDACTED]

[REDACTED]

In case visual disturbances should occur upon instillation of the drop the subject is advised not to drive or use machines until such effects have disappeared.

8.4 Examination Procedures

8.4.1 Procedures to be performed at each trial visit with regard to trial objective(s)

See [Appendix 1](#) for a schedule of visits and measurements in recommended order. [Appendix 3](#) describes the eye examinations. These should not be done earlier than 2 hours after IMP instillation. If possible the same investigator/coordinator should perform the assessments for an individual subject. Primary endpoint assessments at Baseline Visit 1 (Day 1) and Visit 4 (Day 57) should be done preferably on the same time of the day.

The dedicated dosing coordinator will perform tasks as described in IMP Masking7.4.

Visit 0 (Up to 14 days before Visit 1): Screening

- Informed consent / HIPAA;
- Demographic data and medical / medication history;
- Review of inclusion / exclusion criteria;
- Urine pregnancy test;
- Ocular Surface Disease Index (OSDI[©]) questionnaire;
- Visual acuity (ETDRS);
- Slit-Lamp biomicroscopy;
- Tear Film Break-up Time (TFBUT);
- Fluorescein staining (NEI scale);
- Meibomian gland assessment (MGD score) (wait 5 min prior start of Schirmer's test);
- Schirmer's test I (without anesthesia);
- Intraocular pressure;
- Dilated fundoscopy;
- Non-leading AE questioning (Adverse event query);
- Qualified subjects will be scheduled for Visit 1.

Visit 1 (Day 1): Baseline/Randomization

- Previous/Concomitant Medication;
- Review of inclusion / exclusion criteria;
- Urine pregnancy test;
- Dryness Score (VAS Severity of Dryness);
- VAS for burning/stinging, sticky feeling, foreign body sensation, itching, blurred vision, sensitivity to light, pain, frequency of dryness, and awareness of dry eye symptoms;
- Ocular Surface Disease Index (OSDI[©]) questionnaire;
- Visual acuity (ETDRS);
- Slit-Lamp biomicroscopy;
- Tear Film Break-up Time (TFBUT);
- Fluorescein staining (NEI scale);
- Meibomian gland assessment (MGD score) (wait 5 min before start of Schirmer's test);
- Schirmer's test I (without anesthesia);
- Randomization;
- In-office dose of IMP;
- Instillation comfort questionnaire;
- Non-leading AE questioning (Adverse event query);
- Dispensation of dosing diary
- Drug dispensation of one kit for self-administered dosing until Visit 2;
 - Subjects will be instructed on how to administer IMP;
 - Subjects will be instructed to dose with IMP on the day of their next visit at least 2 hours before the start of their visit (Visit 2);
 - Subjects will be instructed on how to complete the dosing diary.

Visit 2 (Day 15 ± 1), Visit 3 (Day 29 ± 2):

- At the beginning of the visit the subject will be asked about the time of last dose. Assessments should be performed at least 2 hours after last dose of IMP;
- Collection and review of IMP and dosing diary;
 - Calculate subject compliance with doses in the subject diary as described in [Section 8.5](#) and re-educate subject as necessary.
- Concomitant medication update;
- Dryness Score (VAS Severity of Dryness);
- VAS for burning/stinging, sticky feeling, foreign body sensation, itching, blurred vision, sensitivity to light, pain, frequency of dryness, and awareness of dry eye symptoms;
- Ocular Surface Disease Index (OSDI[©]) questionnaire;
- Visual acuity (ETDRS);
- Slit-Lamp biomicroscopy;
- Fluorescein staining (NEI scale);
- Non-leading AE questioning (Adverse event query);
- Re-dispensation of dosing diary;

Visit 2 Drug dispensation of one kit for self-administered dosing until Visit 3;

- Subjects will be instructed on how to administer IMP;
- Subjects will be instructed to dose with IMP on the day of their next visit at least 2 hours before the start of their visit (Visit 3);
- Subjects will be instructed on how to complete the dosing diary.

Visit 3 Drug dispensation of two kits for self-administered dosing until Visit 4;

- Subjects will be instructed on how to administer IMP;
- Subjects will be instructed to dose with IMP on the day of their next visit at least 2 hours before the start of their visit (Visit 4);
- Subjects will be instructed on how to complete the dosing diary.

Visit 4 (Day 57 ± 2) or ET:

- At the beginning of the visit the subject will be asked about the time of last dose. Assessments should be performed at least 2 hours after last dose of IMP;
- Collection and review of IMP and diary;
- Concomitant medication update;
- Urine pregnancy test;
- Dryness Score (VAS Severity of Dryness);
- VAS for burning/stinging, sticky feeling, foreign body sensation, itching, blurred vision, sensitivity to light, pain, frequency of dryness, and awareness of dry eye symptoms;
- Ocular Surface Disease Index (OSDI[©]) questionnaire;
- Eyedrop acceptability questionnaire;
- Visual acuity (ETDRS);
- Slit-lamp biomicroscopy;
- Tear Film Break-up Time (TFBUT);
- Fluorescein staining (NEI scale);
- Meibomian gland assessment (MGD score) (wait 5 min before start of Schirmer's test);
- Schirmer's test I (without anesthesia);
- Intraocular pressure;
- Dilated fundoscopy;
- Non-leading AE questioning (Adverse event query);
- Trial exit.

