7 TRIAL MATERIALS

7.1 Investigational Medicinal Product(s)

7.1.1 IMP(s)/ Formulation (s)

NOV03 drug product is a thin, clear, preservative-free ophthalmic solution drop (see [Table 1](#)). Saline eye drops preserved with benzalkonium chloride will be supplied as the control product (see [Table 2](#)). Investigational drug and control will be provided in identical bottles and labels to ensure the double-masked character of the trial.

Table 1 Active Investigational Product

	Investigational Product
Product code:	NOV03
Chemical name:	Perfluorohexyloctane
Molecular formula:	C ₁₄ H ₁₇ F ₁₃
Dosage form:	3 mL ophthalmic solution
Unit dose:	11 µL drop size; 100% perfluorohexyloctane
Route of administration:	Topical ocular administration
Physical description:	Colorless and clear ophthalmic solution
Excipients:	None

Table 2 Control Investigational Product

	Control Investigational Product
Product name:	Saline solution
Chemical name:	Sodium chloride solution (0.6 %)
Molecular formula:	NaCl
Dosage form:	3 mL ophthalmic solution
Unit dose:	35-40 µL drop size
Route of administration:	Topical ocular administration
Physical description:	Colorless and clear ophthalmic solution
Excipients:	0.01% benzalkonium chloride w/v

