10.3 Sample Size

The study has been designed to have at least 95% power to reject both H_{01} and H_{02} assuming independence between the sign and symptom endpoint; positive correlation between these two endpoints would increase the overall power.

Two hundred fifty (250) subjects (study eyes) per treatment group yields 97.9% power to reject H_{01} in favor of H_{A1} and conclude superiority of NOV03 over saline in the mean CFB tCFS score at Day 57 assuming a true difference (NOV03 minus saline) of -1.0, a common standard deviation of 2.8, and a two-sided alpha = 0.05. Two hundred fifty (250) subjects per treatment group yields 97.9% power to reject H_{02} in favor of H_{A2} and conclude superiority of NOV03 over saline in the mean CFB Dryness Score (VAS) at Day 57 assuming a true difference (NOV03 minus saline) of -10, a common standard deviation of 28, and a two-sided alpha = 0.05. Accounting for an assumed 10% subject discontinuation rate, approximately 560 subjects (280 subject each arm) will be randomly assigned to trial treatment such that approximately 250 evaluable participants per arm complete the trial.

Therefore, assuming independence between tCFS score and Dryness Score (VAS), 250 FAS subjects per treatment group at Day 57 yields $97.9\% * 97.9\% = 95.8\%$ power to reject both H_01 and H_02 .

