10.4 Statistical Analysis

10.4.1 General Considerations

Quantitative variables will be summarized using number of subjects (n), mean, median, standard deviation, minimum and maximum. The qualitative variables will be summarized using counts and percentages.

All summaries will be presented by treatment group. Summaries will be provided for demographics, baseline medical history, concurrent therapies, and subject disposition.

For the purpose of summarization, medical history, concurrent therapies, and AEs will be coded to MedDRA and WHO Drug dictionaries, as appropriate.

Baseline measures are defined as the last non-missing measure prior to the initiation of randomized study treatment.

All primary and secondary analyses will be two-sided at a significance level of 0.05.

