13 APPENDICES

Appendix 1 Schedule of Assessments (in recommended order)

Procedure	Visit 0 Within 14 days before Visit 1 (Day -14 to -1)	Visit 1 Day 1	Visit 2 Day 15 ± 1	Visit 3 Day 29 ± 2	Visit 4 / (ET) Day 57 ± 2
Informed Consent / HIPAA	X				
Demographics	X				
Medical/Surgical History	X				
Previous/Concomitant Medication	X	X	X	X	X
Inclusion/Exclusion Criteria	X	X			
Urine Pregnancy Test	X	X			X
Dryness Score (VAS severity of dryness)*		X	X	X	X
VAS*		X	X	X	X
OSDI*	X	X	X	X	X
Eyedrop Acceptability Questionnaire*					X
Visual Acuity (ETDRS)	X	X	X	X	X
Slit-Lamp Biomicroscopy	X	X	X	X	X
TFBUT*	X	X			X
Corneal Fluorescein Staining (NEI scale)*	X	X	X	X	X
Meibomian Gland Assessment (MGD score)*	X	X			X
Schirmer's Test I (without anesthesia)*	X	X			X
Intraocular Pressure	X				X
Dilated Fundoscopy	X				X
Randomization (via IRS)		X			
In-office instillation of randomized IMP		X			
Instillation Comfort Questionnaire		X			
Adverse Event Query	X	X	X	X	X
Dosing Diary Dispensation and/or Review		X	X	X	X
Dispensation of trial medication		X	X	X	
Collection of trial medication			X	X	X
Trial Exit					X

*= Assessment to be conducted in the order as depicted in the Schedule of Assessments; ETDRS = Early Treatment of Diabetic Retinopathy Study; HIPAA = Health Information Portability and Accountability Act; NEI = National Eye Institute; OSDI = Ocular Surface Disease Index; TFBUT = Tear Film Break Up Time; ET= Early Termination; VAS: burning/stinging, sticky feeling, foreign body sensation, itching, blurred vision, sensitivity to light, pain, frequency of dryness, and awareness of dry eye symptoms

[figure not shown]

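### The count of opened bottles in a returned kit all but reveals the arm, and the protocol contradicts itself on when returned bottles are handled and by whom

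*Protocol*

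**What the plan says.** **Products.** Protocol Section 7.1.1 gives 3 mL for both products, with an 11 µL drop for NOV03 and a "35-40 µL drop size" for saline. Appendix 2 calls for one drop per eye four times a day. Section 7.1.4 supplies two bottles per kit, with one kit at Visits 1 and 2 and two kits at Visit 3. Under Section 7.1.5 subjects open one bottle at a time and bring empties back in the kit box.

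**Timing.** In Section 8.4.1 the Visit 2 and 3 list places "Collection and review of IMP and dosing diary" near the top, with compliance calculation and re-education as needed, before the Dryness Score, the other VAS items, OSDI and staining. The Visit 4 list has the same collection and review step in the same place, without the re-education item. Appendix 1 puts diary review and collection of medication below all assessments, as does SAP Table 1. Those rows lack the asterisk that means "Assessment to be conducted in the order as depicted in the Schedule of Assessments".

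**Handler.** Section 7.2 states: "At each visit, subjects will return all bottles to clinic staff for accountability purposes". Section 7.1.4 gives collection at Visits 2 to 4 to the dosing coordinator. Section 7.4 explains why: "Due to physicochemical differences between NOV03 and saline, there will be a dedicated dosing coordinator who will be responsible for the handling of IMP". It also bars that person from other trial procedures and from passing the information on.

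**The concern.** The dosing coordinator role exists because the products can be told apart. Its protection depends on bottles staying with that one person and on subjects rating symptoms without first being drawn into talk about their drops. A site that follows Section 8.4.1 line by line reviews the kit and diary with the bottles at hand, re-educates if needed, and only then takes the Dryness VAS. Section 8.5 says bottles are collected to assess dosing compliance, so the talk itself may differ by arm: a NOV03 subject who dosed correctly hands back unopened bottles, which can prompt questions.

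The ratings that follow include Dryness at Day 15, the first secondary endpoint in the alpha-controlled sequence, and at Visit 4 the primary Dryness Score and burning/stinging, the third secondary endpoint. Separately, if bottles reach site staff other than the coordinator, someone who grades staining could see the count.

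**Working it through.** **The plan's own figure.** The power statement ("Two hundred fifty (250) subjects (study eyes) per treatment group yields 97.9% power to reject" for tCFS) reproduces. The standard error is 2.8 × √(2/250) = 0.250; 1.0/0.250 − 1.96 ≈ 2.03, which corresponds to 97.9%. Dryness (10 and 28) gives the same, and the product is 95.8%. Nothing in this point changes these numbers. The plan gives no figure for bottle use, so that is derived here.

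**Volume used.** Volume = days × 4 doses × 2 eyes × drop size. SAP Section 6.5.5 uses 56 expected doses for the first interval, which is 112 drops. Bottles opened = volume ÷ 3 mL, rounded up.

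| Interval | Drops | NOV03 (11 µL) | Saline (35-40 µL) |
|---|---|---|---|
| Visit 1 to 2, and 2 to 3 (14 days) | 112 | 1.23 mL: 1 of 2 opened | 3.92-4.48 mL: 2 of 2 opened |
| Visit 3 to 4 (28 days) | 224 | 2.46 mL: 1 of 4 opened | 7.84-8.96 mL: 3 of 4 opened |

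Saline use is 35/11 = 3.2 to 40/11 = 3.6 times NOV03 use.

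**How firm the separation is.**
- At 80-120% of expected use over 14 days, NOV03 uses 0.99-1.48 mL (1 bottle) and saline 3.14-5.38 mL (2 bottles).
- At 80-120% over 28 days, NOV03 uses 1.97-2.96 mL (1 bottle) and saline 6.27-10.75 mL (3 or 4 bottles).
- At the extremes of the visit windows and full compliance, Visit 2 to 3 spans 11-17 days: NOV03 0.97-1.50 mL (1 bottle), saline 3.08-5.44 mL (2 bottles). Visit 3 to 4 spans 24-32 days: NOV03 2.11-2.82 mL (1 bottle), saline 6.72-10.24 mL (3 or 4 bottles).
- It breaks down at poor compliance. Over 14 days a saline subject needs only one bottle below 3/3.92 = 77% of expected use (35 µL drop) or 3/4.48 = 67% (40 µL drop). Over 28 days a NOV03 subject needs a second bottle above 3/2.464 = 122%. The 30-day limit on an open bottle in Section 7.1.3 could also lead a NOV03 subject to open a second one in a long last interval.

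**Residual fluid.** After 14 days the open NOV03 bottle holds 3 − 1.23 = 1.77 mL and the second saline bottle 6 − 4.48 = 1.52 to 6 − 3.92 = 2.08 mL. After 28 days it is 0.54 mL against 0.04-1.16 mL in the third saline bottle. These overlap, so the cue is the count.

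**The two contradictions.**

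| Question | One place | Another place |
|---|---|---|
| When is IMP collected and reviewed? | Section 8.4.1: before VAS, OSDI and staining | Appendix 1: after all assessments, order not fixed |
| Who receives bottles? | Section 7.2: clinic staff | Sections 7.1.4 and 7.4: dosing coordinator |

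Section 4.3 makes the listed order binding for symptom assessments and evaluations and points to both Section 8.4 and Appendix 1, so it does not settle the first question.

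**The case against.** The masking design is stronger than one line in Section 7.2 suggests. Sections 7.1.4, 7.4 and 10.6 give IMP accountability and all IMP discussion to a coordinator who may not assess or report, and Section 8.4.1 refers to Section 7.4 before its visit lists. Collecting bottles early therefore tells the staining grader nothing. Section 7.2 itself names the coordinator for inventory, records and reconciliation. This stands: tCFS is exposed only if the words clinic staff are taken literally.

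For the VAS, the rater is the subject, who has used these same bottles at home for 14 or 28 days. Handing them in shows nothing new, and no available passage tells subjects what the other arm consumes. This also stands, and it limits the concern to the conversation before rating. Re-education is listed only for Visits 2 and 3, so the cue is weaker at Visit 4, where both primary endpoints are measured.

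It can also be said that IMP collection is neither a symptom assessment nor an evaluation, so Section 4.3 does not fix its place; that Appendix 1 already has the safer order; and that the operations manual or the redacted parts of Appendix 3 may settle the matter. Those sources are not available. On the text at hand, a site can follow Section 8.4.1 in good faith and review the IMP first.

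A reader might infer that both primary endpoints are exposed to unmasking. The documents do not support that, for the reasons above.

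**Conclusion.** The point holds as two contradictions to reconcile, with a modest but avoidable route to bias. The opened-bottle count is effectively unmasking to whoever sees it: 1 against 2 over 14 days, and 1 against 3 over 28 days. This assumes a 3 mL fill, no waste, and dosing as instructed over nominal intervals; the counts stay apart at 80-120% of expected use.

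The remaining risk to the VAS is talk about the drops with a coordinator who can in effect tell the arm. It bears mainly on Visits 2 and 3, including Dryness at Day 15, and less on Day 57. No size or direction of rating bias can be derived from the documents, and any number of VAS points put on it would be invented. Sample size, power and the testing sequence are unaffected.

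**What to change.** - **Section 8.4.1, Visits 2 to 4:** keep only the time-of-last-dose question at the start. Move IMP collection, diary review and, at Visits 2 and 3, compliance calculation and re-education to after the assessments, as in Appendix 1.
- **Section 8.4.1 and Appendix 1:** state that, apart from that question, nobody discusses the IMP or diary with the subject until the VAS and OSDI are complete. Leave the Visit 4 Eyedrop Acceptability Questionnaire in its fixed place after OSDI and before staining. A ban running through to staining would break that order.
- **Section 7.2:** replace clinic staff with the dedicated dosing coordinator. Sections 4.3 (study staff helping with the diary) and 7.1.5 (clinic staff coaching on dosing) could be aligned with Section 7.4 in the same edit.

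The cost is protocol wording and a memo to sites. The same people do the same tasks in a different order within the visit, and endpoints, sample size and analysis stay as they are.
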